### **ESTIMATING SEVERITY GRADE**

For abnormalities NOT found elsewhere in the tables use the scale below to estimate grade of severity:

| GRADE 1 | Mild; asymptomatic or mild symptoms; clinical or diagnostic observations          |  |  |  |
|---------|---|--|--|--|
|         | only; intervention not indicated  |  |  |  |
| GRADE 2 | Moderate; minimal, local or noninvasive intervention indicated; limiting age-     |  |  |  |
|         | appropriate instrumental ADL*.  |  |  |  |
| GRADE 3 | Severe or medically significant but not immediately life-threatening;             |  |  |  |
|         | hospitalization or prolongation of hospitalization indicated; disabling; limiting |  |  |  |
|         | self-care ADL**.  |  |  |  |
| GRADE 4 | Life-threatening consequences; urgent intervention indicated.                     |  |  |  |
| GRADE 5 | (Death) is not appropriate for some AEs and therefore is not an option.           |  |  |  |

\*Instrumental ADL refer to preparing meals, shopping for groceries or clothes, using the telephone, managing money, etc.

\*\*Self-care ADL refer to bathing, dressing and undressing, feeding self, using the toilet, taking medications, and not bedridden.

[figure not shown]
| Adverse Event                    | GRADE 1          | GRADE 2           | GRADE 3              | GRADE 4           | GRADE 5 |
|----------------------------------|------------------|-------------------|----------------------|-------------------|---------|
| Vaginal inflammation             | Mild discomfort  | Moderate          | Severe discomfort    | Widespread areas  | Death   |
| Definition: A disorder           | or pain with     | discomfort or     | or pain and edema,   | of mucosal        |         |
| characterized by inflammation    | edema or redness | pain with edema,  | or redness; limiting | ulceration; life- |         |
| involving the vagina.            |                  | redness; limiting | self-care ADL;       | threatening       |         |
|                                  |                  | instrumental ADL  | small areas of       | consequences;     |         |
|                                  |                  |                   | mucosal ulceration   | urgent            |         |
|                                  |                  |                   |                      | intervention      |         |
|                                  |                  |                   |                      | indicated         |         |
| Vaginal pain                     | Mild pain        | Moderate pain;    | Severe pain;         | -                 | -       |
| Definition: A disorder           |                  | limiting          | limiting self-care   |                   |         |
| characterized by a sensation of  |                  | instrumental ADL  | ADL                  |                   |         |
| marked discomfort in the vagina. |                  |                   |                      |                   |         |
| Vaginal burning                  | Mild burning     | Moderate          | Severe burning;      |                   |         |
| Definition: A disorder           |                  | burning; limiting | limiting self-care   |                   |         |
| characterized by a sensation of  |                  | instrumental ADL  | ADL                  |                   |         |
| marked burning in the vagina.    |                  |                   |                      |                   |         |
| Vaginal pruritus                 | Mild             | Intense;          | Intense; constant;   | -                 | -       |
| Definition: A disorder           |                  | intermittent;     | limiting self-care   |                   |         |
| characterized by an              |                  | limiting          | ADL or sleep; oral   |                   |         |
| uncomfortable feeling of itching |                  | instrumental ADL  | corticosteroid or    |                   |         |
| and burning in the vagina.       |                  |                   | immunosuppressive    |                   |         |
|                                  |                  |                   | therapy indicated    |                   |         |

#### Appendix C. Study Product Instructions for Use

#### **How to Use the Study Drug**

#### **Description**

• Each single-use foil pouch contains a pre-filled applicator with a pink cap and a plunger rod (Figure 1).

### **Important Use Information**

- During your entire time in this study, use the Study Drug every time you have vaginal sex regardless of the time of the last application or even if you have sex more than once in a day. The Study Drug can be used immediately before or up to one hour before vaginal sex.
- If you or your partner develop burning or irritation of the vagina or penis or experience difficult or painful urination, discontinue use and consult your clinical site staff.

### **Instructions for Using the Study Drug**

1.

- Wash your hands with soap and water before opening the foil pouch.
- Remove the pre-filled applicator and plunger from the foil pouch.
- 2. Gently insert the pointed end of the plunger into the opening inside the pre-filled applicator until the plunger lightly snaps in place (Figure 2). Be careful not to push the plunger farther after it snaps in place to avoid the release of any Study Drug into the cap.

[figure not shown]
[figure not shown]

Figure 2

[figure not shown]
3.

- Remove the pink cap from the pre-filled applicator (Figure 3). The pre-filled applicator is now ready for use.
- NOTE space between the Study Drug and end of the applicator is normal.

[figure not shown]

4.

- Hold the applicator at the grooved area closest to the plunger. Gently place the applicator into the opening of your vagina pushing it as far as it will comfortably go, similar to the placement of a tampon (Figure 4).
- NOTE Lying on your back with your knees up may help with this step.

5. Using your index finger, push the plunger all the way into the barrel of the pre-filled applicator until it stops to ensure all the Study Drug has been applied (Figure 5).

- Gently withdraw the pre-filled applicator (Figure 6). Do not reuse the empty applicator or plunger. Place the used applicator in the resealable plastic bag provided (only one applicator per bag) and return along with all other used and unused applicators to next scheduled visit.
- The Study Drug gel is effective immediately after insertion. Vaginal sex should occur within one hour after insertion.

Figure 6

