# 2 Study Design

Eight hundred forty-four (844) women, ages 18 to 45, who have had a documented urogenital chlamydia or gonorrhea infection at any time over the 16 weeks preceding the Enrollment Visit, or found to be positive at Screening Visit will be enrolled. A high prevalence of *Chlamydia trachomatis* infection has been observed in those who were treated for urogenital chlamydial infection during the preceding several months. The second infection may result from re-infection through an untreated partner or exposure through a new partner. By including only women who have had a CT infection within the past 16 weeks, this study targets those at high risk for infection (1), (26).

Regardless of whether a potential subject agrees to participate in the study, subjects should be treated according to each site's routine standard of care (SOC) for STI prevention which should follow the prevention strategies recommended by the Centers for Disease Control and Prevention (https://www.cdc.gov/std/tg2015/clinical.htm). These strategies include client-centered STI prevention counseling addressing subject's individual risk factors and advice on the correct and consistent use of male condoms to prevent STIs and human immunodeficiency virus (HIV), as well as condom provision if part of the site's SOC. Those who agree to participate (ie, subjects who provide informed consent) should be treated according to SOC prior to and throughout the study period as necessary.

Subjects will be tested for current GC/CT infection by nucleic acid amplification test (NAAT) via vaginal swab. Those negative for current infection will be enrolled. Those who test positive for CT/GC infection will receive SOC treatment. To meet eligibility criteria, these subjects will not be enrolled until 3 to 4 weeks after screening (at least 21 days after treatment).

Eligible participants will be enrolled and randomized 1:1 (422 subjects per treatment arm) to either AMPHORA or placebo; 5 g of AMPHORA or placebo will be supplied in pre-filled, single-dose applicators. A baseline vaginal pH and a full gynecologic exam (speculum) will be obtained at enrollment.

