## 2.1 Study Outcome Measures

#### 2.1.1 Primary Outcome Measures

The primary objective of this study is to demonstrate the superior efficacy of AMPHORA compared with placebo for the prevention of urogenital CT infection. The primary efficacy endpoint is the proportion of subjects who experience at least one CT infection during the study intervention period (incident infection of CT).

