#### 3.5 Blinding

Investigators and subjects in both intervention groups will remain blinded to their intervention assignment (AMPHORA or placebo) over the entire duration of the study (double-blind). The Sponsor, Evofem, Inc., will prepare the investigational product as well as placebo and supply these products in ready-to-dispense status.

Any request from the Investigator for information about treatment administered to study subjects must be approved by the Medical Monitor.

If the code must be broken in the case of an emergency for subsequent management of a subject, the Investigator must provide a written request with record of the circumstances surrounding the event, including the purpose, date, and personnel involved. Emergency unblinding will be available by using the IWRS. An emergency treatment disclosure is a reportable event that must be reported to the Medical Monitor within 24 hours of the event.

Otherwise, blinding will not be broken until all subjects have completed the final study visit and the database has been locked and approved.

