## Placebo (Universal Placebo Gel)

The placebo used in this study is universal placebo gel (UPG). UPG is an isotonic non-buffering gel, with pH adjusted to 4.5 and containing 2.7% hydroxyethylcellulose, sorbic acid, sodium hydroxide, sodium chloride, and purified water. In clinical studies, UPG has been proven safe and acceptable when used up to twice daily for 14 days (27).

**Table 2** Study Product Dosing

| Intervention Group | AMPHORA   | Placebo   |  |  |
|--------------------|---|---|--|--|
| Group A            | 422 subjects, 5 g dose applied up to 1 hour prior to coitus | N/A   |  |  |
| Group B            | N/A   | 422 subjects, 5 g dose applied up to 1 hour prior to coitus |  |  |

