#### 4.1.1 Formulation and Packaging

For this study, pre-filled, single-use applicators will be used. The AMPHORA and placebo gels will be filled (5 g) into identical single-dose applicators consisting of an injection molded opaque white high-density polyethylene (HDPE) barrel with a rounded distal end for easy insertion. A thermoplastic rubber piston will be inserted at the opposite end of the barrel. This component will seal the end of the barrel to keep the contents stable over time and also functions as the applicator piston when in use. A HDPE plunger rod will be packaged alongside of the barrel within an aluminum overwrap. Product will be dispensed as a box of 10 overwrapped applicators with used applicator return bags and instructions for use.

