#### 4.1.6 Administration

AMPHORA and placebo will be intravaginally administered by the subject in exactly the same manner. To administer, the plunger rod is inserted into the piston end of the barrel engaging the piston. The cap is removed from the distal end of the barrel; the barrel is then inserted into the subject's vagina (distal end first). The plunger rod is pushed into the barrel, subsequently moving the piston and gel toward the open end of the barrel. Only the gel will leave the barrel.

Detailed instructions for administration are included as **Appendix** C and supplied to the subject with the investigational product. Subjects will be trained in investigational product application prior to issuance.

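### The use instructions given to women in both arms state that the study gel is effective, which is the question under test and is untrue for placebo.

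*Protocol*

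**What the plan says.** The last application step in Protocol Appendix C (Instructions for Using the Study Drug) contains the sentence "The Study Drug gel is effective immediately after insertion". It has no qualifier and does not say what the gel is effective for.

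Protocol 4.1.6, which covers AMPHORA and placebo together, says that the detailed instructions are "supplied to the subject with the investigational product". Protocol 4.1.1, again for both gels, says: "Product will be dispensed as a box of 10 overwrapped applicators with used applicator return bags and instructions for use".

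Protocol section 2 has the women "randomized 1:1 (422 subjects per treatment arm) to either AMPHORA or placebo". Under Protocol 3.5, "Investigators and subjects in both intervention groups will remain blinded to their intervention assignment".

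Protocol 2.1.1 states: "The primary objective of this study is to demonstrate the superior efficacy of AMPHORA compared with placebo".

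Protocol section 2 also calls for standard-of-care STI prevention at each site, including "advice on the correct and consistent use of male condoms to prevent STIs". Condoms are provided only where that is part of the site's standard of care.

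**The concern.** A blinded trial of an unproven preventive product should not tell participants in writing that the product works. Here the sentence comes with the product, so it is at hand when the woman decides how to protect herself.

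The women are enrolled because a recent infection puts them at high risk of another; Protocol 8.2 assumes that 22.5% on placebo will have a CT infection by Week 16. Condoms alone are not accepted as contraception (inclusion criterion 7), so each woman should already have another contraceptive method. For her, the main remaining reason to use a condom is to avoid infection, which is the benefit she might take the word effective to promise.

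What is at stake is the accuracy of participant information and the chance of false reassurance. Endpoints, analysis and sample size are not involved.

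**Working it through.** No calculation decides this point. The only figure it uses is the split of the sample, so that is checked first and the texts are then compared.

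1. **The plan's sample size (Protocol 8.2).** Inputs: p1 = 0.225, p2 = 0.13, two-sided 5% error, 80% power, and losses of 20%, 15% and 5%.
   - n per arm = [1.960 × √(2 × 0.1775 × 0.8225) + 0.8416 × √(0.225 × 0.775 + 0.13 × 0.87)]² / 0.095² = (1.0591 + 0.4512)² / 0.009025 = 252.7, which rounds up to 253. Power at 253 per arm is 80.04%.
   - Total = 2 × 253 / (1 − 0.40) = 843.3, which rounds up to 844, or 422 per arm. This agrees with the plan.
   - Placebo share = 422/844 = 50%.

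2. **Who reads the sentence.** Sections 4.1.1 and 4.1.6 supply the instructions with either gel. Appendix C is a single version that speaks only of the Study Drug, as blinding requires. All 844 planned women are therefore given it.

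3. **Whether it is supported for AMPHORA.** Prevention of CT transmission is the hypothesis to be tested (Protocol 8.1) and the primary objective (2.1.1). Protocol 4.1 describes the gel as still in development, both as a contraceptive and as a microbicide. The supporting data in section 1.2 are in vitro and from mice. The statement therefore asserts what the trial is meant to find out.

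4. **Whether it is true for placebo.** Protocol 4.1 describes a non-buffering gel adjusted to pH 4.5. The protocol claims no protective effect for it and uses it as the reference against which efficacy is judged. For 422 women the statement is untrue.

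5. **Whether it is needed for timing.** The sentence that follows it sets the one-hour limit. Important Use Information, earlier in the same appendix, already allows use right before intercourse or within the hour before. Deleting the sentence removes no instruction.

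6. **Whether Appendix C corrects it.** The available text does not mention placebo, unproven efficacy or condoms.

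7. **Whether its effect could be measured.** SAP 8.8.4 defines the condom rate over the treatment phase only, and the eDiary is set up at Visit 1 (Protocol Table 1), so it yields no rate from before the study. Both arms receive the same sentence, so there is no unexposed group. The planned summary can describe condom use by arm, but it cannot attribute any change to this wording.

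**The case against.** The strongest defence is context. The sentence closes the application steps and is followed at once by the one-hour limit. Read with that limit, it means that no waiting time is needed after insertion. It does not mention infection or condoms. That is probably what was intended, but a participant reads the words as they stand, and they assert that the gel works.

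The second defence is that women are told the truth elsewhere. Protocol section 12 promises a full discussion of risks and possible benefits and a detailed description of the products in the consent form. Protocol 5.1 has questions answered before consent is completed, and 5.8.3 requires documented training and checked understanding before product is issued. Section 2 extends standard-of-care management through the study. All of this stands as mitigation. The consent pages are not part of the review copy, so one cannot say that women are left misinformed overall. Even so, a correct consent form would then conflict with the insert, and the insert is what comes with the product.

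The third defence, that no fall in condom use is shown, also stands: the documents contain no evidence of one and no figure for its size.

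**Conclusion.** The point holds as a minor one about participant information. An unqualified statement of efficacy goes to all 844 planned women. It is unsupported for the 422 allocated to AMPHORA and untrue for the 422 allocated to placebo. It could falsely reassure women at high risk, but how often is unknown.

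A reader might infer three stronger things that the documents do not support:

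- **That women will replace condoms with the gel.** This is possible, but it is unquantified and is countered by the counselling and consent steps.
- **That the trial result is biased.** The wording is identical in both arms under blinding, so by itself it gives no route to a difference between them. Power and sample size as planned are unaffected.
- **That the eDiary condom data will show whether harm occurred.** They have neither a pre-study rate nor an unexposed comparison.

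The conclusion assumes that one version of Appendix C is used for both gels, as its neutral wording and sections 4.1.1 and 4.1.6 indicate. It also assumes that no caveat is lost with the figures missing from the review copy.

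**What to change.** Delete the sentence from Appendix C. If the sponsor prefers to keep a statement there, replace it with wording that it is not yet known whether the study gel prevents infection, that the gel may be placebo, and that the site's condom advice still applies. Check the new text against the consent form so that the two agree.

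Dose, timing of use, endpoints and analyses do not change. The cost is a wording amendment with IRB approval, which Protocol 11.2 requires for protocol amendments, and replacement of inserts already packed in product boxes.

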### Appendix D. Subject Satisfaction with Product

#### **STUDY VISIT 5**

- 1. How satisfied are you with the study product?
  - a. Very satisfied
  - b. Satisfied
  - c. Somewhat satisfied
  - d. Somewhat dissatisfied
  - e. Dissatisfied
- 2. How likely is it that you would recommend this study product to a friend who is considering such a product?
  - a. Very likely
  - b. Likely
  - c. Somewhat likely
  - d. Somewhat unlikely
  - e. Unlikely
- 3. If you were still considered to be at risk of an infection, how likely would you be to continue with the use of this product if it were available after the study?
  - a. Very likely
  - b. Likely
  - c. Somewhat likely
  - d. Somewhat unlikely
  - e. Unlikely

### Appendix E. Subject Sexual Satisfaction

### **Study Visit 5**

What impact has the study product had on your sex life since your last study visit?

- a. My sex life is a lot better than before
- b. My sex life is a little better than before
- c. My sex life is no different than before
- d. My sex life is a little worse than before
- e. My sex life is a lot worse than before

### Appendix F. Sexual Function Questionnaire (SFQ)

How frequently in the PAST MONTH have you had the problems listed below?\* **ALSO**, MARK THE BOX IN THE LAST COLUMN if the problem stops your sexual activity.

|    |  | Not
at all | Seldom, <25% of the time | Sometimes, about 50% of the time | Usually, about 75% of the time | Always | MARK THE BOX IF THE PROBLEM STOPS YOUR SEXUAL ACTIVITY |
|----|--|---------------|--------------------------|----------------------------------|--------------------------------|--------|--|
| a. | Vaginal dryness
during sexual
activity                   | 1             | 2                        | 3                                | 4                              | 5      |  |
| b. | Lack of sexual interest or desire                              | 1             | 2                        | 3                                | 4                              | 5      |  |
| c. | Vaginal tightness  | 1             | 2                        | 3                                | 4                              | 5      |  |
| d. | Pain during penetration or intercourse                         | 1             | 2                        | 3                                | 4                              | 5      |  |
| e. | Anxiety about your sexual performance                          | 1             | 2                        | 3                                | 4                              | 5      |  |
| f. | Unable to orgasm   | 1             | 2                        | 3                                | 4                              | 5      |  |
| g. | Vaginal bleeding or irritation from penetration or intercourse | 1             | 2                        | 3                                | 4                              | 5      |  |
| h. | Increased sensitivity of your skin to intimate touching        | 1             | 2                        | 3                                | 4                              | 5      |  |
| i. | Sharp pain inside or outside your vagina                       | 1             | 2                        | 3                                | 4                              | 5      |  |
| j. | Other problem with sexuality; Please specify:                  | 1             | 2                        | 3                                | 4                              | 5      |  |

\*Source: Question 10, Sexual Function Questionnaire, Fred Hutchinson Cancer Research Center.

### Appendix G. Female Sexual Function Index (FSFI)

| Female Sexual Function Index (FSFI) ©   |  |                                       |  |  |  |  |
|---|--|---------------------------------------|--|--|--|--|
| Subject Iden  | tifier   | Date                                  |  |  |  |  |
| INSTRUCTIONS: These questions ask about your sexual feelings and responses during the past 4 weeks. Please answer the following questions as honestly and clearly as possible. Your responses will be kept completely confidential. In answering these questions the following definitions apply: |  |                                       |  |  |  |  |
| Sexual activi   | ty can include caressing, foreplay   | masturbation and vaginal intercourse. |  |  |  |  |
| Sexual interd   | Sexual intercourse is defined as penile penetration (entry) of the vagina.   |                                       |  |  |  |  |
|   | Sexual stimulation includes situations like foreplay with a partner, self-stimulation (masturbation), or sexual fantasy.                      |                                       |  |  |  |  |
| CHECK ONI   | Y ONE BOX PER QUESTION.  |                                       |  |  |  |  |
| experience, t   | e or interest is a feeling that includ
feeling receptive to a partner's sex
bout having sex.                                     |                                       |  |  |  |  |
| 1. Over the   | past 4 weeks, how often did you f   | eel sexual desire or interest?        |  |  |  |  |
|   | Almost always or always Most times (more than half the tir Sometimes (about half the time) A few times (less than half the tin Almost never or never | ,                                     |  |  |  |  |
| 2. Over the past 4 weeks, how would you rate your level (degree) of sexual desire or interest?  |  |                                       |  |  |  |  |
|   | Very high
High
Moderate
Low
Very low or none at all  |                                       |  |  |  |  |

Page 1 (of 5)

Sexual arousal is a feeling that includes both physical and mental aspects of sexual excitement. It may include feelings of warmth or tingling in the genitals, lubrication (wetness), or muscle contractions.

| 3. | Over the past 4 weeks, how often did you feel sexually aroused ("turned on") during sexual activity or intercourse? |   |  |  |  |
|----|--|---|--|--|--|
|    |  | No sexual activity Almost always or always Most times (more than half the time) Sometimes (about half the time) A few times (less than half the time) Almost never or never |  |  |  |
| 4. |  | past 4 weeks, how would you rate your level of sexual arousal ("turning sexual activity or intercourse?  |  |  |  |
|    |  | No sexual activity Very high High Moderate Low Very low or none at all  |  |  |  |
| 5. |  | ne past 4 weeks, how confident were you about becoming sexually d during sexual activity or intercourse?   |  |  |  |
|    |  | No sexual activity Very high confidence High confidence Moderate confidence Low confidence Very low or no confidence  |  |  |  |
| 6. |  | past 4 weeks, how often have you been satisfied with your arousal ent) during sexual activity or intercourse?  |  |  |  |
|    |  | No sexual activity Almost always or always Most times (more than half the time) Sometimes (about half the time) A few times (less than half the time) Almost never or never |  |  |  |

| 7. | Over the past 4 weeks, how often did you become lubricated ("wet") during sexual activity or intercourse? |   |  |
|----|--|---|--|
|    |  | No sexual activity Almost always or always Most times (more than half the time) Sometimes (about half the time) A few times (less than half the time) Almost never or never |  |
| 8. |  | past 4 weeks, how difficult was it to become lubricated ("wet") during ctivity or intercourse?   |  |
|    |  | No sexual activity Extremely difficult or impossible Very difficult Difficult Slightly difficult Not difficult  |  |
| 9. |  | past 4 weeks, how often did you maintain your lubrication ("wetness") pletion of sexual activity or intercourse?   |  |
|    |  | No sexual activity Almost always or always Most times (more than half the time) Sometimes (about half the time) A few times (less than half the time) Almost never or never |  |
| 10 |  | past 4 weeks, how difficult was it to maintain your lubrication s") until completion of sexual activity or intercourse?  |  |
|    |  | No sexual activity Extremely difficult or impossible Very difficult Difficult Slightly difficult Not difficult  |  |

About equally satisfied and dissatisfied

Moderately dissatisfied

Very dissatisfied

Copyright ©2000 All Rights Reserved

AMPHORA®

Page 5 (of 5)
